### 9.1. MELD Score

MELD score is derived from the patient's serum total bilirubin, serum creatinine, and INR, as appropriate, to predict survival ([Kamath 2007](#)). MELD score will be calculated and reported for visits where these parameters are measured as described in the protocol. An increasing MELD score is associated with increased severity of hepatic dysfunction and increased 3-month mortality risk.

- Summary statistics of MELD score including baseline values, change from baseline, and Percentage change from baseline values will be presented by treatment group and by each scheduled post-baseline visit.
- Analysis of change from baseline in MELD score will be analyzed using the Wilcoxon Rank Sum Test. The tabulation will include median, interquartile range for each treatment group, median differences and 95% CI of the median differences between treatment groups using the Hodges-Lehmann estimate. If the median differences between treatments are not symmetrical around the median, the Sign Test may be used.
- MELD score will be presented in shift tables showing the shift from baseline to each scheduled post-baseline visit by the count and percentage of patients within each shift classification (<10, 10 to <12, 12 to <13, 13 to <14, 14 to <15, and  $\geq 15$ ).

The MELD Score analyses will be repeated for MELD-Na

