**Table 2: Child-Pugh Scoring System**

Factor	Units	Points		
		1	2	3
Serum bilirubin	µmol/L	<34	34-50	>50
	mg/dL	<2.0	2.0-3.0	>3.0
Serum albumin	g/L	>35	28-35	<28
	g/dL	>3.5	2.8-3.5	<2.8
Prothrombin time	Seconds prolonged	0-3	4-6	>6
	INR	<1.7	1.7-2.3	>2.3
Ascites		None	Mild	Moderate-Severe
Hepatic encephalopathy a		0	Grade 1 or 2	Grade 3 or 4

a Grade 0: normal consciousness, personality, neurological examination, electroencephalogram  
 Grade 1: restless, sleep disturbed, irritable/agitated, tremor, impaired handwriting, 5 cps waves  
 Grade 2: lethargic, time-disoriented, inappropriate, asterixis, ataxia, slow triphasic waves  
 Grade 3: somnolent, stuporous, place-disoriented, hyperactive reflexes, rigidity, slower waves  
 Grade 4: unrousable coma, no personality/behavior, decerebrate, slow 2-3 cps delta activity  
 (Pugh 1973, Lucey 1997), Vilstrup 2014

- Baseline CP score is calculated based on components measured at Screening visit.
- Summary statistics of CP score including baseline values, change from baseline, and percentage change from baseline values will be presented by treatment group and by each scheduled post-baseline visit.
- Analysis of change from baseline in CP score will be analyzed using the Wilcoxon Rank Sum Test. The median differences and 95% CI of the median differences between treatment groups will be constructed using the Hodges-Lehmann estimate. If the median differences between treatments are not symmetrical around the median, the Sign Test may be used.
- CP class (A, B, and C) will be presented in a shift table showing the shift from baseline to each scheduled post-baseline visit by the count and percentage of patients within each shift classification (A, B, and C).
- Components of CP score categories as listed in Table 2 will be summarized by the count and percentage of patients within each category at baseline and each scheduled post-baseline visit.

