#### 10.3.4. TEAE Analyses

The counts and percentages of subjects experiencing a TEAE and TEAEs by PTs and SOCs in the following categories will be presented by study treatment arm:

All AE summaries will be restricted to TEAEs. Each AE summary will be displayed by treatment group for DB phase, DBext phase, and combined. Summaries that are displayed by SOC and PT will be ordered by descending order of incidence of SOC and PT within each system organ class.

Summary tables of the following TEAEs will be presented:

- Overall summary of TEAEs
- Patient incidence of TEAEs and the total number of entries by SOC and PT. This summary will be repeated for subgroups specified in [Section 10.10](#).
- Patient incidence of TEAEs by SOC, PT, and highest severity. At each level of patient summarization, a patient is classified according to the highest severity if the patient reported 1 or more events. AEs with missing severity will be considered severe for this summary.
- Patient incidence of TEAEs by SOC, PT, and closest relationship to IP (Related/Not Related). Related AEs are those with relationships reported as “Definite,” “Probable,” or “Possible,” and unrelated AEs are those with relationships reported as “Unlikely” or “Not Related”. At each level of patient summarization, a patient is classified according to the closest relationship if the patient reported 1 or more events. AEs with a missing relationship will be considered related for this summary.
- Patient incidence of serious TEAEs and the total number of entries by SOC and PT.
- Patient incidence of TEAEs leading to IP withdrawal or study discontinuation by SOC and PT. This is a subset of the AEs where Action Taken with Study Treatment is checked as “Drug Withdrawn” or where “Patient Discontinued from Study” is checked on the eCRF.
- Patient incidence of COVID-19 related TEAEs.

Patient incidence will be summarized as subject counts and percentages unless otherwise specified.

The number of AEs and events per 100 patient years will be summarized by SOC and PT.

- Individual patient years = (the last recorded study visit date – first dose date +1)/365.25  
where: the last recorded study visit date = end of study date recorded on end of study CRF page for that patient
- Total patient years on study = sum of all individual patient years within the Safety Population
- Events per 100 patient years =  $\frac{\text{Number of Event} \times 100}{\text{Total Patient Years on Study}}$

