## **APPENDIX A. DATA PRESENTATION CONVENTIONS:**

Unless otherwise specified, the baseline value for analyses of all parameters is defined as the last non-missing value prior to the first administration of investigational product.

For categorical variables, the number and percentage of subjects within each category of the parameter, including a category for missing data, will be presented. Percentage calculations will be based on the analysis population, unless otherwise specified.

For continuous variables, summary statistics will include the number of subjects and the mean, standard deviation (SD), standard error of the mean (SE), median, 25th and 75th quartiles, minimum, and maximum values.

All statistical analyses will be performed using SAS statistical software Version 9.4 or higher unless otherwise noted.

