### **General Methods**

- Summaries will be presented for each treatment and overall for subjects disposition, demographics and baseline characteristics, medical history, disease history, prior medications, and historical procedures summary tables. Summaries will be presented for each treatment for other tables.
- All subjects and relevant data entered into the database will be included in subject data listings, including screen failures, where applicable.
- All data listings that contain an evaluation date will contain a relative study day as defined in below.
- For categorical variables, summary tabulations of the number and percentage of patients within each category of the parameter will be presented. Percentage calculations will be based on non-missing data, unless otherwise specified. Percentages are rounded to 1 decimal place, unless otherwise specified. The category for missing data will not have percentage.
- For continuous variables, the number of patients, mean, standard deviation (SD), standard error of the mean (SE), median, Q1, Q3, minimum, and maximum values will be presented. The precision of summary statistics, unless otherwise, specified will be as follows:
  - minimum, maximum: same decimal place as the raw data,
  - mean, median, Q1, and Q3: 1 more decimal place than the raw data,
  - SD and SE: 2 decimal places more than the raw data.
- In general, the decimal places should not exceed 3 decimal places unless appropriate. 95% confidence intervals (CIs) will be provided and will be rounded to 1 decimal place.

- For results from an analysis of covariance (ANCOVA) model or a mixed model repeated measures (MMRM), least square (LS) mean and LS mean difference will be presented with one decimal place, and standard error (SE) of LS means and SE of LS mean difference will be presented with two decimal places.
- p-value will be presented with 3 decimal places.
- Time-to-event data will be summarized using Kaplan-Meier (KM) methodology using 25th, 50th (median), and 75th percentiles with associated 2-sided 95% CIs.

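### Appendix A sets two contradictory default denominators for percentages, and the extension-phase safety tables have no denominator or person-time of their own

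*SAP*

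**What the plan says.** **Percentages.** The opening text of SAP Appendix A (Data Presentation Conventions) states that "the number and percentage of subjects within each category of the parameter, including a category for missing data, will be presented", and then: "Percentage calculations will be based on the analysis population, unless otherwise specified". General Methods, in the same appendix, states "Percentage calculations will be based on non-missing data, unless otherwise specified" and adds "The category for missing data will not have percentage".

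**By-visit tables.** Section 9.1: "MELD score will be presented in shift tables showing the shift from baseline to each scheduled post-baseline visit by the count and percentage of patients". Section 9.2: "CP class (A, B, and C) will be presented in a shift table showing the shift from baseline to each scheduled post-baseline visit", again with counts and percentages. Neither section names a denominator. Efficacy tables use the ITT Population, which is everyone randomized who took any IP (Sections 4.2 and 9). Missing values are not imputed (Appendix A, Missing Data).

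**Extension phase.** Section 10.3.4: "Each AE summary will be displayed by treatment group for DB phase, DBext phase, and combined". Sections 10.8 and 10.9 ask for the same split for concomitant medications and procedures. Section 10 places safety analyses on the Safety Population, defined in Section 4.3 as all patients with at least one dose. Section 4 defines no extension population. For event rates, Section 10.3.4 counts each patient's time from first dose to the end-of-study date and sums it over the Safety Population, without dividing it by phase.

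**The concern.** Both Appendix A sentences are current text, both are general defaults for categorical variables, and neither is narrower than the other, so neither can serve as the exception that the other allows. They disagree on the denominator and on whether missing data carry a percentage. They part company exactly for patients who have no value at the visit, such as those who have withdrawn, died or been transplanted. In moderate to severe hepatic impairment such patients are not a detail.

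The extension tables raise a related problem. A patient who stopped before the extension cannot have an event in it, yet sits in the Safety Population. Time before the extension cannot contain an extension event, yet is in the patient-years.

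Safety and tolerability against placebo is a primary objective (Section 2.1.1). There is no formal hypothesis (Section 2.2), and Section 10 generally plans no inferential safety comparison. Descriptive percentages and rates are therefore the main safety result. With about 25 patients per arm, a handful of patients moves them visibly. If the rule is left open, it will be chosen at programming.

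**Working it through.** The SAP states no percentage that could be reproduced; what is in question is the rule. The only relevant arithmetic in the plan is the sample size in Section 3.3: 30 + 20 = 50 patients at 1:1, so 25 per arm. That is consistent.

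**Step 1: is either default overridden for the shift tables?** Sections 9.1 and 9.2 give no denominator. Section 5 does give one, for disposition only. A patient lost before Week 48 stays in the ITT Population and has no imputed category, so is in the denominator under the first rule and out of it under the second.

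**Step 2: size within one arm.** Inputs: 25 patients and, for illustration, 5 in one Week 48 shift cell. Section 3.3 gives 15% discontinuation, stated for PK sizing; the higher rates are assumptions. Number seen = 25 × (1 − rate), rounded. Analysis-population rule = 5/25. Non-missing rule = 5/seen.

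| Lost by Week 48 | Seen | Analysis population | Non-missing | Gap (points) |
|---|---|---|---|---|
| 15% (SAP) | 21 | 20.0% | 23.8% | 3.8 |
| 25% (assumed) | 19 | 20.0% | 26.3% | 6.3 |
| 40% (assumed) | 15 | 20.0% | 33.3% | 13.3 |

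**Step 3: size between arms.** With 5 such patients in each arm, the difference under the analysis-population rule is always 0.0 points. Under the non-missing rule it depends on retention:
- 21 and 21 seen: 0.0 points.
- 19 and 23 seen (assumed): 26.3% − 21.7% = 4.6 points.
- 17 and 23 seen (assumed): 29.4% − 21.7% = 7.7 points.

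**Step 4: DBext incidence.** If n of 25 patients enter the extension, incidence on the Safety Population is lower than incidence among entrants by the factor 25/n: 1.19 for n = 21, 1.32 for n = 19 and 1.67 for n = 15.

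**Step 5: DBext events per 100 patient-years.** Assumptions: 10 extension events; 21 patients complete 48 weeks and enter; 4 leave on average halfway through. Then 48 weeks = 336/365.25 = 0.920 years, and time before the extension = 21 × 0.920 + 4 × 0.460 = 21.2 patient-years.

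| Extension follow-up (assumed) | Whole-study patient-years | DBext patient-years | Rate, SAP definition | Rate, DBext time |
|---|---|---|---|---|
| 0.5 year | 31.7 | 10.5 | 31.6 | 95.2 |
| 1 year | 42.2 | 21.0 | 23.7 | 47.6 |
| 2 years | 63.2 | 42.0 | 15.8 | 23.8 |

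**The case against.** The best case for leaving this alone is that little is lost. Both rules present counts and refer to a missing category, so a reader can recompute either percentage. No hypothesis is tested. The between-arm MELD and Child-Pugh comparisons are Wilcoxon tests with Hodges-Lehmann estimates, and death, transplant, MELD of 15 or more and hospitalised decompensation have their own time-to-event analyses in Section 9.6. All of this stands, and it limits the point to descriptive tables. It does not make two opposite rules into one.

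Several stronger readings are tempting and are not supported:

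- A reader might infer that the non-missing rule flatters the arm that loses its sickest patients. The direction is not fixed. In Step 3, if the cell is an unfavourable one, the arm with more loss looks worse under that rule. If the lost patients would themselves have been in the cell, it could look better. The SAP gives no loss by arm.
- A reader might infer that the ITT denominator is the correct one. It counts lost patients as not being in the category, which is the same kind of dilution that is objectionable in the extension tables. Which default to keep is a preference.
- A reader might infer that extension incidence will certainly be diluted. Section 10.3.4 states no denominator for its phase tables, and a programmer might restrict them to entrants. The SAP does not say so; taken literally, Sections 4.3 and 10 lead to the whole Safety Population. Section 5 does count patients who completed the Week 48 visit, but does not make that count a denominator.
- A reader might extend the point to exposure and compliance. Sections 10.1 and 10.2 build these from doses taken in the phase, so patients without extension dosing largely have no value there.

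**Conclusion.** The contradiction in Appendix A is certain from the text, and Sections 9.1 and 9.2 do not resolve it. At the SAP's own 15% figure, borrowed from PK sizing, it moves a 20.0% cell to 23.8%. With equal loss in both arms and equal counts it creates no difference between them; larger or unequal gaps rest on assumed losses.

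The extension point follows from the literal text. Incidence is understated by a factor of 1.19 if 21 of 25 patients enter. In the one-year illustration the event rate is about half what extension time alone would give (23.7 against 47.6 per 100 patient-years).

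These effects are confined to descriptive tables. The Wilcoxon, ANCOVA/MMRM and time-to-event results do not change. The text should be corrected, but the point does not put the trial's analyses in doubt.

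**What to change.** 1. In Appendix A, delete one of the two default sentences, together with its statement on the missing category, so that a single rule applies. Which one stays is the sponsor's choice. In the by-visit MELD and Child-Pugh shift tables, state the denominator and show the number missing per arm.
2. For DBext tables of adverse events, concomitant medications and procedures, use as denominator the patients who took at least one IP dose in the DBext phase. Compute DBext events per 100 patient-years on DBext time only.

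The cost is SAP wording and table shells. The disposition and dosing records already hold what is needed, and no new data are collected.

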### **General Methods**

- Summaries will be presented for each treatment and overall for subjects disposition, demographics and baseline characteristics, medical history, disease history, prior medications, and historical procedures summary tables. Summaries will be presented for each treatment for other tables.
- All subjects and relevant data entered into the database will be included in subject data listings, including screen failures, where applicable.
- All data listings that contain an evaluation date will contain a relative study day as defined in below.
- For categorical variables, summary tabulations of the number and percentage of patients within each category of the parameter will be presented. Percentage calculations will be based on non-missing data, unless otherwise specified. Percentages are rounded to 1 decimal place, unless otherwise specified. The category for missing data will not have percentage.
- For continuous variables, the number of patients, mean, standard deviation (SD), standard error of the mean (SE), median, Q1, Q3, minimum, and maximum values will be presented. The precision of summary statistics, unless otherwise, specified will be as follows:
  - minimum, maximum: same decimal place as the raw data,
  - mean, median, Q1, and Q3: 1 more decimal place than the raw data,
  - SD and SE: 2 decimal places more than the raw data.
- In general, the decimal places should not exceed 3 decimal places unless appropriate. 95% confidence intervals (CIs) will be provided and will be rounded to 1 decimal place.

- For results from an analysis of covariance (ANCOVA) model or a mixed model repeated measures (MMRM), least square (LS) mean and LS mean difference will be presented with one decimal place, and standard error (SE) of LS means and SE of LS mean difference will be presented with two decimal places.
- p-value will be presented with 3 decimal places.
- Time-to-event data will be summarized using Kaplan-Meier (KM) methodology using 25th, 50th (median), and 75th percentiles with associated 2-sided 95% CIs.

## Key Definitions

### First Dose Date

First dose date is defined as the day of first dose of IP received after randomization.

### Last Dose Date

Last dose date is defined as day of the last dose of IP. For subjects ongoing at time of analysis, last dose date will be considered the date of the most recent study visit in the database for that subject.

### Study Day

The study day is determined relative to the date of first dose of IP. The day of the first dose of IP will be defined as study day 1. The day prior to the first dose of IP is study day -1. There is no study day 0.

For events that occur before the first dose of IP, study day = date of the event – first dose date; for events that occur on or after the first dose of IP, study day = date of the event – first dose date + 1.

### Time to Event

The time to an event will be calculated in days as the date of the first occurrence of the event - the date of first IP administration + 1.

The time to a pre-treatment adverse event will be calculated as the date of first IP administration - the date of the first occurrence of the adverse event.

### Baseline and Change from Baseline

The baseline value for statistical analyses of quantitative parameters is defined as the mean of all available evaluations prior to the first administration of IP, unless otherwise specified. Values collected at unscheduled visits prior to the start of the IP administration will be included in the calculation of baseline values. If there is only one evaluation prior to the first administration of IP then the available data from this evaluation will be used as the baseline value.

The baseline value for analyses of lipid parameters is defined as the last fasted evaluation prior to the first administration of IP.

The baseline value for analyses of qualitative parameters (eg, normal/abnormal) is defined as the last evaluation prior to the first administration of IP.

Baseline values defined above will not change regardless if a subject stops taking IP and begins taking commercially marketed OCA.

Change from baseline = (post-baseline value – baseline value).

Percent change from baseline =  $100 * (\text{post-baseline value} - \text{baseline value}) / \text{baseline value}$

For the purpose of tabulations, the unscheduled post-baseline values generally will be excluded from summary tables, but will be included in data listings. Unscheduled visits will be considered for analyses of shift from baseline to worst value (low-normal-high).

### **Dose Regimen**

Following the discussion in [Section 3](#), dose regimen for each clinical visit after first dose up to Week 12 Visit is OCA 5 mg once weekly; dose regimen after Week 12 Visit could be OCA 5 mg once weekly for patient not up-titrated or OCA 5 mg twice weekly for patient up-titrated; and dose regimen after Week 18 Visit could be OCA 5 mg once weekly, 5 mg twice weekly, or 10 mg twice weekly based on patient titration (up-titrated or down-titrated) history prior to the visit. For example, if an up-titration to 5 mg twice weekly is given to a patient at Week 12 Visit, this regimen should be the one for this patient at Week 18 visit.

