## 11.3. Handling of Missing Data, BLQ Data, or Data Exclusions

Missing concentration data for all patients who are administered scheduled study treatments will be considered as non-informative missing and will not be imputed. No concentration estimates will be provided for missing sample values.

For all analyses (drug concentrations and PK parameters), the following rules will apply:

- Concentration values below the assay's lower limit of quantification (BLQ) will be imputed to zero
- The sampling time of pre-dose samples relative to dosing will also be treated as zero

Examples of potential reasons for exclusion of data from PK summary analyses include, but are not limited to:

- Subject not fasted for 8 hours prior to PK visit;
- Subject not adhering to standardized meal timing (or missed meal) during 24-hour PK profile collection;
- Non-standard dosing (eg, drug holiday, altered dose level, altered dose frequency) used prior to PK visit.

Data excluded based on this review will be included in listing outputs but will be excluded from summary tables.

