## 12. PHARMACODYNAMIC ANALYSES

The ITT Population will be used for all PD analyses. Baseline is defined as the mean of all available evaluations before treatment.

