**12.3.3. Listings and Summary Tables for PD Data**

Plasma concentrations for individual bile acid subcomponent and total concentrations (unconjugated, glyco-conjugate, tauro-conjugate, and total) for UDCA, CDCA, DCA, CA, and LCA will be listed for each subject, and summarized using descriptive statistics at baseline and at each study visit stratified by baseline CP category (CP-B, CP-C, and Combined) and treatment (Placebo, 5 mg QW, 5 mg BIW, and 10 mg BIW, Combined OCA).

Total bile acids (sum of all unconjugated and conjugated bile acids for UDCA, CDCA, DCA, CA, and LCA), total endogenous bile acid (sum of all unconjugated and conjugated bile acids for CDCA, DCA, CA, and LCA), as well as concentrations of C4 and FGF-19 will also be listed for each subject and summarized using descriptive statistics at baseline and at each study visit stratified by baseline CP category (CP-B, CP-C, and Combined) and treatment (Placebo, 5 mg QW, 5 mg BIW, and 10 mg BIW, Combined OCA).

All listings and summary tables will include change from baseline and percent change from baseline data for each study visit. Additional PD analyses may be performed, if warranted by the data.

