### **Missing Data**

All available data of the subjects who withdraw from the study for any reasons will be analyzed. Missing data will be assumed to be missing at random. There will be no imputation of missing data for the analysis purpose. Change from baseline of an endpoint will be missing when either baseline value of the endpoint is missing or post-baseline value of the endpoint is missing.

Incomplete start and end dates for adverse events and concomitant medications are imputed as follows:

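### The by-regimen PD tables have no off-drug category, so OCA-arm samples taken while IP is interrupted or stopped, or after a switch to commercial OCA, would be summarized as on-dose values

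*SAP*

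**What the plan says.** Appendix A (Dose Regimen) is where the SAP defines the regimen at a visit. For the early visits it is categorical: "dose regimen for each clinical visit after first dose up to Week 12 Visit is OCA 5 mg once weekly". After the Week 12 Visit the regimen depends on whether the patient was up-titrated, and after Week 18 it "could be OCA 5 mg once weekly, 5 mg twice weekly, or 10 mg twice weekly based on patient titration (up-titrated or down-titrated) history prior" (meaning before that visit).

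Section 12.3.3 summarizes the PD biomarkers at baseline and each visit by Child-Pugh category and "treatment (Placebo, 5 mg QW, 5 mg BIW, and 10 mg BIW, Combined OCA"). Section 12 sets the analysis set: "The ITT Population will be used for all PD analyses". Section 4.2 analyzes that population by randomized treatment. Section 12.3.1 excludes PD samples only when fasting was not confirmed.

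For PK, Section 11.3 lists, among examples of possible reasons for exclusion from summaries, "Non-standard dosing (eg, drug holiday, altered dose level, altered dose frequency) used prior to PK visit". The PD section has no counterpart.

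On patients who leave study treatment, Appendix A says "Baseline values defined above will not change regardless if a subject stops taking IP and begins taking commercially marketed OCA", and its Missing Data section adds "All available data of the subjects who withdraw from the study for any reasons will be analyzed".

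**The concern.** A column headed 10 mg BIW will be read as the biomarker response of patients taking that regimen. A patient who interrupts or stops IP has not been titrated, so a rule built on titration history leaves the last active label in place. The rule has no other label to give, and the PD section has no exclusion to catch the sample.

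C4, FGF-19 and bile acids serve a secondary objective (Section 2.1.2), and Section 12.1 treats them as markers of FXR activation. Section 13 drops the planned PK/PD correlation analysis, so these tables are the main description of PD by dose that remains. Off-drug samples would pull a regimen's values toward no effect. They would also gather under whichever regimen patients were on when they stopped, so the pattern across doses could shift as well as its level.

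**Working it through.** The SAP states no figure to reproduce here, so the main check is to trace the rules for one kind of visit.

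**1. Can such visits occur?** Section 10.1 defines temporary IP discontinuation, with discontinuation and restart dates, and subtracts it from exposure. Section 5 tabulates withdrawal from treatment separately from withdrawal from the study, and also reports study status after treatment. Appendix A foresees a patient stopping IP and starting commercial OCA, and keeps the baseline fixed. That provision matters only if later values are still analyzed.

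**2. What label does the visit get?** Take an OCA patient titrated to 10 mg twice weekly who interrupts IP and attends the next scheduled PD visit. Titration history gives 10 mg twice weekly. If the interruption falls before the Week 12 Visit, the label is 5 mg once weekly by the categorical rule.

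**3. Is the sample removed from the PD summary?** The patient is in the ITT Population. If fasting is confirmed, no stated PD rule excludes the sample. It enters the regimen column and Combined OCA.

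**4. Illustration of size.** Inputs from Section 3.3: about 50 patients, 1:1 allocation, at least 20% Child-Pugh C.

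- OCA arm: 50 / 2 = 25.
- Child-Pugh C at the 20% minimum: 0.20 × 50 = 10, so about 10 / 2 = 5 on OCA. That leaves 25 − 5 = 20 Child-Pugh B on OCA.
- With k off-drug patients among n, and an assumed off-drug change of zero: reported mean change = (1 − k/n) × on-drug mean change.

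The last column assumes an on-drug change of −50%; the SAP gives no expected effect.

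| OCA cell | n | k | Shrinkage k/n | −50% would read |
|---|---|---|---|---|
| Combined OCA | 25 | 1 to 4 | 4% to 16% | −48% to −42% |
| Child-Pugh B | 20 | 1 to 4 | 5% to 20% | −47.5% to −40% |
| Child-Pugh C | 5 | 1 | 20% | −40% |
| Child-Pugh C | 5 | 2 | 40% | −30% |

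These cells are not yet split by regimen. The split makes them smaller, so one off-drug patient weighs more.

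**The case against.** The strongest reply is that this is a gap in wording, not a demonstrated distortion. The later part of the Dose Regimen text says what the regimen could be, and it nowhere states that off-drug visits keep the last label. PD samples are scheduled pre-dose and only to Week 48, while double-blind treatment runs on beyond that, so switches to commercial OCA may fall after the last PD sample. Whether patients who have stopped IP still give PD samples is a matter for the protocol. The Missing Data sentence concerns withdrawal from the study, and those patients' data may all be on-drug. Section 12.3.3 is descriptive, and the subject listings, including the date of last treatment (Section 5), would let a careful reader find samples taken after permanent stopping.

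Much of this stands as a limit on certainty and size. It does not remove the point: the text up to Week 12 is categorical, temporary interruptions are plainly expected, and neither the regimen definition nor the PD table offers another place for such a sample. Listings do not correct a summary column.

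Four stronger readings might be inferred, and the SAP does not support them:

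- *The Placebo column is in error if a placebo patient takes commercial OCA.* Keeping that patient under Placebo follows from analysis by randomized treatment in Section 4.2. The Dose Regimen rule, which lists only OCA regimens, does not cause it.
- *The between-arm comparison is affected by the labelling.* Section 9.4 compares treatment groups with a Wilcoxon test and does not use regimen.
- *The same visit would be dropped from PK and kept in PD.* It could be, but Section 11.3 gives examples of potential reasons, so PK exclusion is not automatic.
- *About 15% of samples would be off drug.* The 15% in Section 3.3 is a discontinuation rate assumed for the PK sample size. Patients who leave contribute missing data, not off-drug samples.

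**Conclusion.** The point holds for the descriptive by-regimen OCA summaries in Section 12.3.3. Followed as written, the SAP places OCA-arm PD samples from interrupted, stopped or commercial-OCA visits under an active study regimen and under Combined OCA, so those columns would not describe on-dose values. This is inferred from the absence of any other category or exclusion; the SAP does not say it outright.

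Off-drug samples would tend to dilute the columns. Commercial OCA in the OCA arm makes the label wrong, with a bias of unknown direction. The size cannot be computed, because the SAP gives no interruption or switch rates and no expected PD effect. The 20% and 40% for Child-Pugh C rest on three assumptions: about 5 such patients on OCA, one or two of them sampled off drug, and no off-drug change. The point is worth settling before database lock, but it does not touch the PK summaries or the randomized comparison.

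**What to change.** In Appendix A (Dose Regimen), add two visit flags:

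- *Off IP*, when the visit falls between a recorded temporary discontinuation date and the restart date, or after permanent discontinuation. State how the boundary dates are treated. Do not define the flag by a fixed interval since the last dose: PD samples are pre-dose troughs, normally taken about one dosing interval after the previous dose, so such a cut-off would mislabel adherent patients who attend slightly late.
- *Commercial OCA*, from its recorded start.

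In Section 12.3.3, show flagged OCA-arm samples in a separate row and in the listings, and leave them out of the 5 mg QW, 5 mg BIW, 10 mg BIW and Combined OCA on-dose summaries. Keep the Placebo column and the Section 9.4 comparison by randomized arm under ITT, with a footnote for any placebo samples taken on commercial OCA.

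The cost is a short change of wording and one derived variable. Section 10.1 already relies on the interruption and restart dates, and the start of commercial OCA should be available from the concomitant medication data (Section 10.8). The downside is that some small PD cells lose a few samples.
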